### 2.7.1 Center Heterogeneity

Consistency of treatment effect across centers will be tested within each of the three studies (BIOFLOW-II, BIOFLOW-IV and BIOFLOW-V). To assess consistency of treatment effect size across study centers, Bayesian models will be employed for the subject level data. Any study center with less than 5 subjects per treatment group will be pooled with other study centers by geographic region prior to carrying out this assessment.

Individual data for treatment  $i$  ( $i=1$  for Xience and  $i=2$  for Orsiro), study  $j$  ( $j = 1$  for BIOFLOW-V,  $j = 2$  for BIOFLOW-II and  $j = 3$  for BIOFLOW-IV) and individual  $k$  will be assumed to follow a Bernoulli distribution:

$$Y[i, j, k] \sim \text{dbern}(p[i, j, \text{center}[k]])$$

where center is an index variable that indicates the center that the individual  $k$  was recruited in.

The assumptions are based on a similar model to the model proposed in Legrand et al.. The event rate is assumed to have an additive effect for center that varies within study:

$$\text{logit}(p[i, j, \text{center}[k]]) = \delta[j, \text{center}[k]] + \gamma[j, \text{center}[k]] * (i = 2)$$

The two random effects can be interpreted as the influence of the center on the overall TLF rate in study  $j$  and on the overall treatment effect, respectively. The center effects  $\delta[j, \text{center}[k]]$  and  $\gamma[j, \text{center}[k]]$  in study  $j$ , are assumed to be exchangeable and a priori to follow a normal distribution with mean  $\mu_{\delta}[j]$  and  $\mu_{\gamma}[j]$  and standard deviation  $\sigma_{\delta}[j]$  and  $\sigma_{\gamma}[j]$ , respectively. A uniform prior on (0.1, 10) will be assumed on the random effect variances in study  $j$  ( $\sigma_{\delta}[j]$  and  $\sigma_{\gamma}[j]$ ) Gelman et al. Independent weakly informative  $N(0, 100)$  priors will be assumed for  $\mu_{\delta}$ 's and  $\mu_{\gamma}$ 's. The standard deviation of the random effects can be viewed as a measure of heterogeneity across centers and treatment effect. A value of 1 for standard deviation of random effects '...corresponds to substantial heterogeneity.' Spiegelhalter et al.; therefore, if in BIOFLOW-V the



posterior probability that  $\sigma\_gamma[1]>1$  exceeds 0.85 and the credible intervals discussed above indicate the interaction is qualitative in nature, then this may preclude all sites from being pooled for the primary analysis, in which case the primary analysis may be re-run excluding study centers causing the interaction. A similar determination will be made for BIOFLOW-II and BIOFLOW-IV selected subjects that are included in the Bayesian ITT analysis.

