The two random effects can be interpreted as the influence of the center on the overall TLF rate and on the overall treatment effect, respectively. The center effects, $\delta[\text{center}[k]]$ and $\gamma[\text{center}[k]]$, are assumed to be exchangeable and a priori to follow a normal distribution with mean μ_{δ} and μ_{γ} and standard deviation σ_{δ} and σ_{γ} , respectively. As recommended by Geltman et al. 1995⁵¹ uniform prior on (0.1, 100) will be assumed on the two variances. The standard deviation of the random effects can be viewed as a measure of heterogeneity across centers and treatment effect. As indicated in Spiegelhalter 2004 (Spiegelhalter, D.J., Abrams, K.R. and Myles, J.P. (2004). Bayesian Approaches to Clinical Trials and Health-Care Evaluation, John Wiley and Sons, page 169) a value of 1 for standard deviation of random effects ‘...corresponds to substantial heterogeneity.’, therefore, if the posterior probability that $\sigma_{\delta} > 1$ or $\sigma_{\gamma} > 1$ exceeds 0.85 and the credible intervals discussed above indicate the interaction is qualitative in nature, then this may preclude all sites from being pooled for the primary analysis, in which case the primary analysis may be re-run excluding study centers causing the interaction. Additional details will be provided in the full SAP.

Region (US/OUS) heterogeneity

To assess consistency of treatment effect size across regions (United States [US] vs. Outside United States [OUS]) region and an interaction of region and treatment will be included in the model. For the interaction coefficient, we will calculate p_{int} as the 2-sided posterior probability of observing an interaction value that is more extreme than 0. This value is similar to a traditional p-value. If $p_{int} < 0.15$ we will conclude that heterogeneity across region is significant and the treatment effect will be calculated and tested within region.

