## 2.6 Statistical Analysis Sets

### 2.6.1 Intention to Treat (ITT) Analysis Population

The Intent-to-Treat (ITT) population is defined as all randomized subjects. Subjects are analyzed according to the stent to which they were randomized (regardless of the actual stent that they received). This is the primary analysis population.

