## 2.7 Analysis of Primary Endpoint

This study will assess non-inferiority of the 12-month TLF rate for the Orsiro stent vs. the Xience stent. The analysis will be carried out on the ITT set (primary), modified ITT and PP analysis sets. The null hypothesis  $H_0$  is that the Orsiro stent will have a primary endpoint (12-month TLF) rate equal to or exceeding that of the Xience group by the non-inferiority margin or more. The alternative hypothesis  $H_A$  is that the Orsiro stent will have a 12-month TLF rate less than the Xience group rate plus the non-inferiority margin. The hypothesis is defined as follows:

$$\begin{aligned} H_0: \pi_X^V - \pi_O^V &\leq -\delta \\ H_A: \pi_X^V - \pi_O^V &> -\delta \end{aligned}$$

where  $\pi_O^V$  is the true 12-month TLF rate for the Orsiro stent,  $\pi_X^V$  is the true 12-month TLF rate for the Xience arm, and  $\delta$  is the non-inferiority margin chosen to be 0.0385 (or 3.85%) as noted in section 2.5.2, Non-Inferiority Margin.

The proposed model is a Bayesian hierarchical model that assumes a bias between the 12-month TLF rates in BIOFLOW-II and BIOFLOW-V as well as BIOFLOW-IV and BIOFLOW-V studies.

Estimation of the parameters and hypotheses testing of the primary hypotheses is based on the posterior distribution of the parameters. The posterior distribution for parameters which do not have closed form posterior inferences will be carried out by sampling from the posterior distribution of the parameters. The freely available program OpenBUGS (Bayesian inference using Gibbs Sampling) will be used to obtain samples from the posterior distribution of the parameters. Using OpenBUGS, 100,000 samples will be obtained from the posterior distribution of 12-month TLF rates after the initial 5,000 will be discarded. To decrease autocorrelation, only every tenth sample will be used in calculations.

We will check convergence of the MCMC sampler using the Brooks-Gelman-Rubin method. Convergence of the sampler will be established if the ratio of within-chain and between-chain variability for multiple chains starting at different initial values will be close to 1.

The percent of posterior samples that satisfy  $\pi_X^V - \pi_O^V > -\delta$  will be used to estimate the posterior probability of the alternative hypothesis will be calculated and reported in the table below.

Table reporting the posterior probability of the Alternative Hypothesis:

Alternative Hypothesis	Posterior Probability

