Orsiro is non-inferior to Xience ( $\pi_X^V - \pi_O^V > -\delta$ )	XX.X%

This probability will be contrasted against  $\pi^* = 0.975$  as outlined in Section 2.4.

In addition the posterior means and standard deviations of the parameters will be reported along with 95% Credible Intervals as outlined in the table below.

Table reporting the posterior summaries of the 1-year TLF rates in BIOFLOW-V:

	Mean	SD	Lower Bound 95% Credible Interval	Upper Bound 95% Credible Interval
$\pi_X^V$	X.XX	X.XX	X.XX	X.XX
$\pi_O^V$	X.XX	X.XX	X.XX	X.XX

In addition, an adjusted Bayesian analysis based on multivariable hierarchical logistic regression adjusted for age, diabetes, history of PCI, ischemic status and LVEF will be performed. Treatment effect with logistic regression is expressed on the log ODDS ratio scale. The value of non-inferiority margin used for the non-inferiority test on the log ODDS scale in the adjusted analyses is obtained by transforming the probability-scale non-inferiority margin of 0.0385 to the log-odds scale. The transforming is achieved using the formula:

$$\log\{(0.07 + 0.0385) / (1 - 0.07 - 0.0385)\} - \log\{0.07 / (1 - 0.07)\} = 0.481$$

Thus, for the adjusted analyses, the non-inferiority will be met if

$$P(\text{logit}(\pi_X^V) - \text{logit}(\pi_O^V) > -0.481 | \text{Data}) > 0.975$$

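### If the center-heterogeneity trigger is met, SAP 2.7.1 allows the primary analysis to be re-run without centers picked from their TLF results, and neither document says which result then decides

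*SAP*

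**What the plan says.** SAP 2.7.1 fits a hierarchical logistic model to subject-level TLF, with a center effect on the event rate (delta) and on the treatment effect (gamma). Two conditions together trigger action in BIOFLOW-V: the posterior probability that sigma_gamma exceeds 1 must be above 0.85, and "the credible intervals discussed above indicate the interaction is qualitative in nature". If both hold, "then this may preclude all sites from being pooled for the primary analysis", and "the primary analysis may be re-run excluding study centers causing the interaction". The step also reaches the borrowed data: "A similar determination will be made for BIOFLOW-II and BIOFLOW-IV selected subjects" included in the Bayesian ITT analysis.

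Protocol 8.8 gives the same permission ("in which case the primary analysis may be re-run excluding study centers causing the interaction") and leaves further detail to the SAP. Its trigger is met by either sigma_delta or sigma_gamma.

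On the deciding analysis, SAP 2.6.1 says of ITT: "This is the primary analysis population". SAP 2.7 adds: "The analysis will be carried out on the ITT set (primary), modified ITT and PP analysis sets". The posterior probability of non-inferiority is then tested: "This probability will be contrasted against" 0.975.

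**The concern.** A center can be held responsible for a treatment-by-center interaction only by looking at its TLF results in each arm, so the exclusion depends on outcome. Once the trigger is met there are two candidate primary results, and the choice between them would be made after those results are known. The SAP Addendum opens the superiority analysis only if non-inferiority is met, so the same choice could also open a superiority claim.

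Two controls on the step are missing. The condition for a qualitative interaction points back to credible intervals, but no center-level interval is described; the only ones set out earlier in the SAP are for the two overall TLF rates in 2.7. There is also no rule for identifying a responsible center or for how many may be removed.

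The step sits badly with SAP 2.6.4, where BIOFLOW-II and BIOFLOW-IV subjects are selected before BIOFLOW-V database lock by an independent statistician who has not seen outcomes. Section 2.7.1 would then allow some of them to be removed because of their outcomes.

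**Working it through.** **1. Reproduce the design.** Inputs from SAP 2.5 and Protocol 8.1 and 3.5:
- BIOFLOW-V 800:400 evaluable; margin 0.0385; threshold 0.975; log-odds bias SD 0.3.
- BIOFLOW-IV 370:185, weight 1 - 0.20 = 0.8, simulated.
- BIOFLOW-II weight 1 - 0.30 = 0.7, held at its reported rates: 0.065 x 287 = 18.7, taken as 19; 0.080 x 148 = 11.8, taken as 12.

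For each arm, the posterior of the BIOFLOW-V rate is proportional to the BIOFLOW-V binomial likelihood times the discounted likelihood of each historical trial, with the bias, Normal(0, 0.3), integrated out. Success is P(pi_X - pi_O > -0.0385) > 0.975. The null is 7% vs 7% + 3.85% = 10.85%; the alternative is 7% vs 7%. Result: type I error 3.7%-4.2% and power 89.2%-89.8%, against 4.0% and 89.6% stated.

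**2. How often is the 0.85 condition met?** The SAP 2.7.1 model was fitted by MCMC with 20 or 40 equal centers and a baseline-rate center SD of 0.3 (both assumed).
- Homogeneous effect: 0 of 1,600 BIOFLOW-V datasets (upper 95% limit about 3/1,600 = 0.2%). For BIOFLOW-II and BIOFLOW-IV, at most 1 of 400 in any setting tried.
- True center SD 1: 17% (20 centers) and 11% (40 centers). A second simulation with 100 datasets per setting gave 17% and 12%.
- SD 1, also requiring a center's 95% credible interval to exclude zero in the direction opposite to the overall effect: 6.5% and 0.5%. Requiring only that some center's posterior mean be opposite left 17% and 11%.

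**3. What if a re-run decided?** One center was removed in every trial, ignoring the trigger, with no true heterogeneity, 20 to 80 equal centers and 20,000 replicates each. Eighty is the most that the pooling rule allows (400 Xience / 5).

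| Center removed | Type I error | Power, 7% vs 7% |
|---|---|---|
| None | 3.7%-4.2% | 89.4%-89.8% |
| Worst for Orsiro | 6.4%-9.3% | 93.5%-95.4% |
| Best for Orsiro | 1.4%-1.8% | 79%-83% |
| Opposing the overall direction | 1.8%-2.0% | 79%-83% |

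The number removed matters. In the second simulation, dropping the worst 1, 2 or 3 of 20 centers gave 8.8%, 14.8% and 22.3% (4.2% with none dropped); of 40 centers, 7.6%, 11.9% and 17.3% (4.1% with none dropped).

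For BIOFLOW-II, removing one of its 24 centers in every trial moved 4.0% to 4.5% (worst for Orsiro) or 3.2% (best).

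**4. All-center error under real heterogeneity.** With center SD 1 and the average Orsiro rate held at 10.85%, all-center type I error was 15.5% (20 centers) and 10.2% (40), because the primary model has no center term. Dropping the single worst center in every trial raised these to 33% and 21%.

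**The case against.** The strongest reply is that the deciding analysis is already named. ITT means all randomized subjects and is labelled primary in both documents, its posterior probability is the one set against 0.975 in SAP 2.7, and a re-run that may happen presupposes a first run. This stands as the default reading, and a claim that the documents leave the primary population open would be wrong. It does not settle the matter. Section 2.7.1 speaks of the primary analysis itself and says that pooling all sites for it may be ruled out. Where the SAP means a sensitivity analysis it says so (2.6.4, 2.7.3). Nor does 0.975 mark out the deciding run, since the adjusted model in 2.7 and the exponential model in 2.8 use it too.

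The second reply is that the trigger is demanding. An SD of 1 on the log-odds scale spreads 95% of center odds ratios over about exp(2 x 1.96) = 50-fold, and a qualitative interaction is needed as well. This stands. A reader might note that the Uniform(0.1, 10) prior alone puts 9/9.9 = 0.909 on values above 1, already past 0.85, and infer that the rule fires by default. The simulations in step 2 show that it does not.

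The third reply concerns direction. At the null the overall result is against Orsiro, so a center causing a qualitative interaction would normally favor Orsiro, and removing it lowers error to about 2%. This also stands. A reader might infer from the table that the plan inflates error to 6%-9%. The documents do not support that: they do not say that the worst center for Orsiro would go, that removal would happen in every trial, or that the re-run would decide. Nor are these figures bounds, because the text speaks of centers in the plural.

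Finally, the contrast between 17% or 11% and 6.5% or 0.5% should not be pressed. The looser version uses a posterior mean, which is not a credible interval, and only the 95% level was tried.

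**Conclusion.** The point holds as a conditional one. If the trigger is met, the plan permits an outcome-dependent exclusion of centers from an analysis that it still calls primary, and does not say which result decides. Under the planning assumptions the effect is nil: the 0.85 condition almost never fires and the stated 4.0% stands. At a true center SD of 1 the condition is met in about 11%-17% of trials before the qualitative test. If a re-run then decided, type I error and power could move in either direction, according to which centers were removed and how many.

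Type I error for the full sequence of trigger, qualitative judgement, removal and decision was not calculated, and cannot be without the missing rules. The figures rest on assumed numbers of equal-sized centers; real pooled units may be fewer and unequal. The change is worth making because it closes a choice made after outcomes are known, at almost no cost.

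The Protocol and SAP differ in the trigger (either SD against sigma_gamma only) and in the prior (0.1-100 against 0.1-10). Because the Protocol deferred details to the SAP, this is a minor alignment point, not a defect. The prior range changed none of the trigger rates.

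**What to change.** Add to SAP 2.7.1, and to Protocol 8.8 at its next amendment:

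> The all-center ITT analysis alone decides primary non-inferiority success, whatever the heterogeneity result. Any re-run excluding centers, in BIOFLOW-V or in the borrowed BIOFLOW-II/IV data, is a sensitivity analysis and does not affect that decision or open the superiority test.

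In SAP 2.7.1, replace the back-reference to credible intervals with a named center-level interval, for example the 95% credible interval for each pooled center's gamma, and state what pattern makes the interaction qualitative. Align the Protocol trigger and prior with the SAP when the Protocol is next amended.

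The cost is two sentences per document, one definition, and one sensitivity table if the trigger is met. No data or sample size are affected. Waiting for the next amendment avoids a separate submission under Protocol 12.8. There are two limits. A center with aberrant outcomes stays in the primary result unless it is excluded for a documented reason unrelated to outcome. And the change does not bring type I error back to 4.0% where real center heterogeneity exists: all-center error was about 10%-16% at a center SD of 1.

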### 2.7.2 Region (US/OUS) Heterogeneity

To assess consistency of treatment effect size across regions (United States [US] vs. Outside United States [OUS]), region and an interaction of region and treatment will be included in the Bayesian model for the BIOFLOW-V study. For the interaction coefficient, we will calculate

$$p_{int} = 2 * \min\{P(\beta_{int} > 0|Data), p(\beta_{int} < 0|Data)\}$$

as the 2-sided posterior probability of observing an interaction value that is more extreme than 0. This value is similar to a traditional p-value. If  $p_{int} < 0.15$  we will conclude that heterogeneity across region is significant and the treatment effect will be calculated and tested within region.

### 2.7.3 Sensitivity Analysis

A sensitivity analysis will be performed on the primary endpoint on the ITT population. TLF will be re-defined as all cardiac death, ARC-defined myocardial infarction (MI), or clinically driven target lesion revascularization (TLR). A Bayesian analysis will be performed on the composite event rate, and a frequentist analysis will be performed on TLF rates and its components.

## 2.8 Handling of Missing Data in the Analysis of Primary Endpoint

Every effort will be undertaken to limit premature discontinuations and ascertain completeness of data collection. The following analysis strategies will be adopted to handle missing data with results compared for consistency prior to carrying out the above analysis:

- 1) Only subjects who experienced the primary endpoint (TLF at 12 months) or who had appropriate follow-up (at least 330 days post baseline, given the 30-day visit window allowed around the 12-month visit) will be included in the analysis.
- 2) All subjects will be included in the analysis set including data for subjects missing primary endpoint status due to not experiencing the event and not reaching at least 330 days of follow-up. Data for these subjects will be included as 'NA'. Bayesian method will be used for the imputation. A model will be used for the event probabilities:

$$Y[i, j, k] \sim \text{dbern}(p[i, j, k])$$

with

$$\text{logit}(p[i, j, k]) = \beta * X[k] + \text{logit}(p[i, j])$$

where  $X[k]$  are predictors values for subject  $k$ . A noninformative prior will be assumed on the slope parameters  $\beta$  and similarly to the analysis of the primary endpoint, bias will be assumed between TLF rates in different studies.

The following variables will be included in the model as covariates:

- Age (>75, <=75)
- Gender
- Diabetes
- Lesion length (>26 mm, <=26mm)
- RVD (>2.75mm, <=2.75mm)

- 3) Time to event analysis using a Bayesian time to event exponential regression analysis. The protocol specifies that time to event analysis using a Bayesian Cox regression analysis will be performed as a sensitivity analysis but subsequently we determined that an exponential regression is better for allowing incorporating a bias term between the log hazard rates in BIOFLOW-V and BIOFLOW II and BIOFLOW-IV. For each study, a separate hazard ratio comparing Xience to Orsiro stent will be included. Similar to the method proposed as a primary method, a bias will be assumed between the log hazard of BIOFLOW-II or BIOFLOW-IV and the log hazard of the BIOFLOW-V.

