8.9. Handling of Missing Data in the Analysis of Primary Endpoint

Every effort will be undertaken to limit premature discontinuations and ascertain completeness of data collection. The following analysis strategies will be adopted to handle missing data with results compared for consistency prior to carrying out the above analysis:

1. Only subjects who experienced the primary endpoint (TLF at 12 months) or who had appropriate follow-up (at least 330 days post baseline, given the 30-day visit window allowed around the 12-month visit) will be included in the analysis.
2. All subjects will be included in the analysis set including data for subjects missing primary endpoint status due to not experiencing the event and not reaching at least 330 days of follow-up. Data for these subjects will be included as 'NA'. A model will be used for the event probabilities:

$$Y[i, j, k] \sim dbern(p[i, j, center[k]])$$

with

$$\text{logit}(p[i, j, center[k]]) = \beta * X[k] + \text{logit}(p[i, j])$$

where $X[k]$ are predictors values for subject k . A noninformative prior will be assumed on the slope parameters β and similarly to the analysis of the primary endpoint, bias will be assumed between TLF rates in different studies.

The following variables will be included in the model as covariates:

- Age
 - Gender
 - Diabetes
 - Lesion length
 - Others (the complete set will be detailed in the full SAP)
3. Time to event analysis using a Bayesian Cox regression analysis. For each study, a separate hazard ratio comparing Xience to Orsiro stent will be included. Similar to the method proposed as a primary method, a bias will be assumed between the hazard ratio of BIOFLOW-II or BIOFLOW-IV and the hazard ratio of the BIOFLOW-V. Further details will be provided in the full SAP.

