⁴ Smith SC Jr, Dove JT, Jacobs AK *et al.* ACC/AHA guidelines of percutaneous coronary interventions (revision of the 1993 PTCA guidelines) –Executive summary. A report of the American College of Cardiology/American Heart Association Task Force on Practice Guidelines (committee to revise the 1993 guidelines for percutaneous transluminal coronary angioplasty). *J Am Coll Cardiol* 2001;37:2215–2239.

MYOCARDIAL INFARCTION – PROTOCOL DEFINITION⁵

I. PCI (PERCUTANEOUS CORONARY INTERVENTION)

la. Baseline Biomarkers of Myocardial Damage

Periprocedural < 48 hours post PCI

A. Baseline CKMB and Troponin < 1*URL
 
Appropriate cardiac enzyme data:
 
a1. Confirmed by :
 
 - CKMB > 3*URL or - in the absence of CKMB, Troponin > 3*URL or - in the absence of CKMB and Troponin: CEC decision upon clinical scenario

B. Baseline CKMB or Troponin > 1*URL
 
Appropriate cardiac enzyme data:
 
b1. Confirmed by :
 
 - A rise in CKMB $\geq 50\%$ above the previous level and > 3* URL or - In absence of CKMB, a rise in Troponin $\geq 50\%$ above the previous level and > 3*URL. - in the absence of CKMB and Troponin: CEC decision upon clinical scenario 
AND
 
b2. Evidence that cardiac biomarker values were decreasing (e.g., two samples at least 4 hours apart) prior to the suspected MI.

C. New pathologic q waves in 2 contiguous ECG leads

URL = upper range limit, defined as 99th percentile of normal reference range

lb. If Baseline Biomarkers of Myocardial Damage: CK and/or CKMB > 1*URL or acute MI in progress

Myocardial infarction, re-infarction (extension) < 48 hours post PCI

A. If CK (or CKMB) from index MI has not yet reached its maximum level:
 
 - Recurrent thoracic chest pain or ischemia equivalent > 20 minutes (or new ECG changes consistent with MI)

⁵ Adapted from Vranckx P, Cutlip DE, Mehran R, Kint PP, Silber S, Windecker S, Serruys PW. Myocardial infarction adjudication in contemporary all-comer stent trials: Balancing sensitivity and specificity. Addendum to the historical MI definitions used in stent studies. *EuroIntervention* 2010;5:871–874.

AND

- Appropriate cardiac enzyme data:
 - A rise in CK within 24 hours of the index event $> 2 \times \text{URL}$ (confirmed by either CKMB or Troponin $> 1 \times \text{URL}$) and $\geq 50\%$ above the previous level or

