### 2.5 Sample Size Determination

The BIOFLOW-V trial will assess non-inferiority of the 12-month TLF rate for the Orsiro stent vs. TLF rate in subjects treated with the Xience stent. The null hypothesis  $H_0$  is that the Orsiro stent will have a primary endpoint (TLF) rate equal to or exceeding that of the Xience group by the non-inferiority margin or more. The alternative hypothesis  $H_A$  is that the Orsiro stent will have TLF rate less than the Xience group rate plus the non-inferiority margin. Specifically:

$$\begin{aligned} H_0: \pi_X^V - \pi_O^V &\leq -\delta \\ H_A: \pi_X^V - \pi_O^V &> -\delta \end{aligned}$$

Where  $\pi_O^V$  is the true 12-month TLF rate for the Orsiro stent,  $\pi_X^V$  is the true 12-month TLF rate for the Xience arm, and  $\delta$  is the non-inferiority margin.

The assumptions for this analysis are:

- True 12-month TLF rate is 7.0% in both treatment groups ( $\pi_X^V = \pi_O^V$ ).
- Power is 89%.
- 3.85% is the absolute non-inferiority margin (55% relative non-inferiority margin).
- Discount the results of the BIOFLOW-IV data by 20% and BIOFLOW-II data by 30%.
- Standard deviation of the bias terms between the odds of BIOFLOW-II TLF 12-month rates and odds of BIOFLOW-V 12-month rates is 0.3.
- Standard deviation of the bias terms between the odds of BIOFLOW-IV TLF 12-month rates and odds of BIOFLOW-V 12-month rates is 0.3.
- Non-inferiority assessment will be assessed using the posterior probability of the alternative hypothesis as specified above, where  $\pi^* = 0.975$

Rejection of the null hypothesis signifies that the Orsiro stent is not inferior to the Xience stent with regards to 12-month TLF. A total of 1,200 subjects (800 in the Orsiro group and 400 in the Xience group) will have 89.6% power to reject the above null hypothesis in favor of the alternative under the stated assumptions. To account for loss to follow-up (expected to be approximately 10%), a total of 1,334 subjects will need to be randomized. The one-sided type I error estimates are 4.0%, 3.3%, and 4.2% if the actual odds for the 12-month TLF rate of event in the Xience group of the BIOFLOW-IV study are the same, 10% lower and 10% higher when compared with the odds for the 12-month TLF rate of event in the Xience group of the BIOFLOW-V study.

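### Missing-data strategy 2 imputes a full 12-month TLF risk to subjects known to be event-free at last contact, so it largely repeats strategy 1 and adds little as a check on loss to follow-up

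*SAP*

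**What the plan says.** SAP 2.8 lists four strategies for missing primary-endpoint status and asks that their results be compared for consistency.

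- **Item 1** is a complete-case rule: "Only subjects who experienced the primary endpoint (TLF at 12 months) or who had appropriate follow-up (at least 330 days post baseline", with the 330 days explained by the visit window.
- **Item 2** keeps everyone. Its missing group is "subjects missing primary endpoint status due to not experiencing the event and not reaching at least 330 days of follow-up". It then says "Data for these subjects will be included as 'NA'. Bayesian method will be used for the imputation". Each outcome is Bernoulli, with logit p equal to a covariate term plus the logit of the arm-by-study rate. "The following variables will be included in the model as covariates" introduces age, gender, diabetes, lesion length and RVD. No term uses time of last contact.
- **Item 3** is an exponential time-to-event model that handles censoring.
- **Item 4** is a tipping-point analysis.

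Protocol 8.9 item 2 has the same rule ("Data for these subjects will be included as 'NA"'). Protocol Appendix B has a separate category of MI headed "Periprocedural < 48 hours post PCI", so part of TLF can occur in the first two days.

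**The concern.** By item 2's own definition, every missing subject had no TLF up to last contact. The model discards that fact. A subject who leaves event-free at day 300 gets the same TLF probability as a comparable subject at day 0, including a peri-procedural MI risk already survived.

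The probability being fitted is also too high. Subjects with an early event stay in the observed data whatever their follow-up, while event-free subjects with the same short follow-up become missing. Missingness therefore depends on the outcome, and five baseline covariates cannot correct for that.

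Non-cardiac death is the clearest case. It is not a TLF, and death is a reason for study exit in Protocol 5.3.2. If it occurs before day 330, the literal rule marks the subject 'NA' and imputes a possible TLF that can no longer happen.

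At stake is the value of item 2 as a sensitivity analysis. Agreement between items 1 and 2 would be largely built in and would say little about whether loss to follow-up matters.

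**Working it through.** **Inputs from the documents.** SAP 2.5: "True 12-month TLF rate is 7.0% in both treatment groups"; "To account for loss to follow-up (expected to be approximately 10%), a total of 1,334 subjects will need to be randomized"; margin 3.85 points. The plan's own figure reproduces: 1,200 / (1 - 0.10) = 1,333.3, rounded up to 1,334.

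**Assumptions not in the documents.** Loss is uniform over days 1-330. A share f of TLF (0 to 70%) falls within 48 hours and the rest is spread evenly to day 360. Loss is independent of risk.

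**Step 1: 'NA' outcomes carry no information.** A missing Bernoulli outcome sums out of the likelihood. Take an illustrative arm with 60 TLFs in 840 known outcomes, 93 missing and a Beta(1,1) prior. The posterior mean is 61/842 = 7.24% however many subjects are 'NA'. Gibbs sampling gave 7.24% (SD 0.89%) with the 93 imputed and 7.25% (SD 0.90%) for complete cases. Without covariates, item 2 is item 1. Covariates move it only so far as the missing subjects' baseline profile differs.

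**Step 2: bias in an arm's rate.** Let R = 0.07 and d = the proportion lost. A lost subject is followed on average for 165/360 = 0.458 of the year.

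- Observed events: E = R[(1 - d) + d(f + 0.458(1 - f))]
- Known event-free: C = (1 - d)(1 - R)
- Item 1 rate, and item 2 rate without covariates: E/(E + C)
- Missing: M = 1 - E - C
- Their true remaining risk: 0.542·R·d(1 - f)/M

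With d = 0.10 and f = 0: E = 0.0662, C = 0.8370, rate = 0.0662/0.9032 = 7.33%. M = 0.0968, and remaining risk = 0.00379/0.0968 = 3.9%.

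| f | Item 1/2 rate | Remaining risk | Ratio | 'NA' of 1,334 | Imputed TLFs | Expected TLFs |
|---|---|---|---|---|---|---|
| 0 | 7.33% | 3.92% | 1.9 | 129 | 9.5 | 5.1 |
| 0.5 | 7.52% | 2.00% | 3.8 | 127 | 9.5 | 2.5 |
| 0.7 | 7.60% | 1.21% | 6.3 | 126 | 9.5 | 1.5 |

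In simulation, imputing from the conditional risk returned 7.0%.

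**Step 3: individual exits vary widely.** Under a constant hazard, the remaining risk at day t is 1 - 0.93^((360 - t)/360): 6.44% at day 30, 3.56% at day 180, 1.20% at day 300 and 0.62% at day 329. Against 7%, the ratios are 1.09, 1.96, 5.8 and 11.

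**Step 4: the treatment difference.** The formula in step 2 is applied to each arm with the same true 7.0%.

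| Loss, Orsiro / Xience | f = 0 | f = 0.7 |
|---|---|---|
| 10% / 10% | 0 | 0 |
| 3.7% / 3.9% (BIOFLOW-II) | 7.114 - 7.121 = -0.007 points | 7.208 - 7.221 = -0.012 points (rounded) |
| 8% / 13% (illustrative) | 7.26 - 7.44 = -0.19 points (rounded) | 7.47 - 7.81 = -0.34 points |

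The BIOFLOW-II figures come from Protocol 8.1: 287 of 298 Orsiro and 148 of 154 Xience subjects completed 12 months, so non-completion was 11/298 = 3.7% and 6/154 = 3.9%.

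**The case against.** The strongest reply is that item 2 is one of four strategies and its neighbours cover the gap. Item 3 uses the event-free time that item 2 discards, and applies the same margin to 12-month rates. Item 4 sets all missing Xience subjects to no TLF and moves missing Orsiro subjects to TLF one at a time, which stresses the opposite direction far harder. This stands: loss to follow-up is tested elsewhere. It does not rescue item 2. Item 3 is also only a partial substitute, because its constant hazard gives about 7.2-7.4% for a true 7.0% when a third to 70% of TLF is peri-procedural. Item 4 offers no plausible number of missed events to set the tipping count against.

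Second, 10% is a planning allowance. Protocol 5.3.2.1 bars exit as lost to follow-up before the 12-month visit, and BIOFLOW-II lost under 4% per arm, almost equally. This also stands, and it makes a material effect on the difference unlikely.

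Third, the equality of items 1 and 2 is shown here without covariates, and no check fitted the five in the plan. That is why the claim is that item 2 largely reproduces item 1, not that it must match it exactly.

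A reader might go further and infer a fixed inflation factor, a threat to the non-inferiority conclusion, or a missing-data plan that fails as a whole. The documents support none of these. They give no timing from which to fix a factor, they give no reason to expect unequal loss, and items 3 and 4 remain.

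**Conclusion.** The point holds for SAP 2.8 item 2 and Protocol 8.9 item 2, and only there. The stated rule ignores known event-free follow-up, imputes a full 12-month risk and so adds little to item 1. Read literally, it also imputes possible TLF after non-cardiac death.

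Under the assumptions listed in the working (10% loss, uniform drop-out, 0-70% of TLF within 48 hours), the imputed risk averages about 1.9 to 6 times the remaining risk, and each arm's rate is overstated by about 0.3 to 0.6 points. The bias in the difference is close to zero with equal loss. It moves towards non-inferiority only if Xience loss is higher, by about -0.2 to -0.35 points at 8% against 13%. That is roughly 5-9% of the 3.85-point margin, and the split is illustrative with no source in the documents. With higher Orsiro loss the sign reverses. The change is worth making because it gives item 2 a purpose, not because the primary conclusion is likely to depend on it.

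**What to change.** In SAP 2.8 item 2:

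1. Impute each missing BIOFLOW-V subject from P(TLF by 12 months | event-free at last contact).
2. Use a parsimonious piecewise hazard with at least two intervals, 0-48 hours and after 48 hours. Share its time shape across arms and studies. Keep the existing covariates and one arm-level bias term per historical study.
3. Code non-cardiac death before 12 months as no TLF.
4. Apply the existing 3.85-point rule to the resulting BIOFLOW-V 12-month rates.

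A finer grid fitted separately by arm and study is not advisable. Four intervals by two arms by three studies would be 24 baseline risks, and BIOFLOW-II Xience has only about 12 events (8.0% of 154). SAP 2.6.4 also admits historical subjects only with an event or at least 330 days, so the imputation should be confined to BIOFLOW-V.

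The cost is SAP wording and a change to one OpenBUGS model. Last-contact dates are already needed for the 330-day rule and for item 3. Patients and sample size are unaffected. The downside is one or a few extra shape parameters, and an assumed common time shape, in one sensitivity analysis.
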